3.3.2 Clinical Study TR01 in Hemodialysis Patients and Healthy Volunteers

Pruritus is a frequently identified sign and symptoms of uremia (“uremic pruritus”) and is thus a common symptom in patients receiving hemodialysis (Pisoni et al 2006 and Narita et al 2006). Study TR01 was undertaken to assess the safety, PK, and the open label effects on pruritus intensity in hemodialysis subjects. PK and safety was compared to matched healthy control subjects.

Study TR01 was a single site, open label, non-randomized, parallel group, escalating dose study in hemodialysis patients with pruritus of at least mild intermittent intensity receiving intermittent hemodialysis three times a week compared to matched healthy control patients. All subjects were in house during the entire dosing period. Nalbuphine HCl ER tablets were administered orally for up to a 15 day period in HD subjects and 13 days in healthy subjects. Doses were sequentially escalated from 30 mg QD on Day 1 to 30mg BID then to 60 mg BID, 120 mg BID, 180 mg BID and 240 mg BID with dose escalation predicated on PK, safety, and tolerability of the preceding dose. HD subjects remained at each dose level for 2-3 days for a minimum of 4-5 consecutive doses. Healthy subjects remained at each dose level for 3-4 days for a minimum of 5 consecutive doses.

Study subjects were separated into 2 cohorts: Of the 15 HD subjects in enrolled into Cohort 1, 11 were assigned to dose escalate up to 180 mg BID and 4 were assigned to dose escalate up to 240 mg BID. 13 subjects (11 males and 2 females) completed the study. One male subject discontinued secondary to non-drug related disease progression diagnosis of pleural effusion at the 30 mg BID dose level and a female subject discontinued following a Grade 3 AE of vertigo at the 240 mg BID dose level. Cohort 2 were healthy subjects who were assigned to dose escalate up to 180 mg BID. Cohort 2 consisted of 8 healthy subjects (6 males and 2 female) who completed the study and one male subject who discontinued at the 120 mg BID dosing level with only Grade 1 intensity AEs. All study subjects were closely monitored for AEs throughout the study.

In healthy subjects, the dosing regimen resulted in mainly Grade 1 AEs and the dose escalation was tolerable in 8/9 subjects dosed. Of the nine healthy subjects enrolled, one subject withdrew from the study secondary to AE Grade 1 level gastrointestinal reflux, nausea/vomiting and vertigo symptoms at the 120 mg BD dosing level. The subject recovered from the AE following drug discontinuation. AEs that occurred in greater than two subjects were somnolence (N=2), headaches (N=2), flatulence (N=2) and constipation (N=3).

In the HD subjects, there were no deaths or drug-related serious AEs. There were no dose-limiting AEs reported as defined as two HD subjects experiencing a drug-related AE of Grade 3. A total of 72 AEs were reported in the 15 HD subjects of Cohort 1. The nervous and gastrointestinal organ systems had the highest incidence of AEs. The most frequently occurring AEs were nausea and somnolence. Of the 13 HD subjects who completed the study (10 HD patients assigned to dose up to 180 mg BID and 3 HD subjects assigned to dose up to 240 mg BID), 12 subjects completed the trial per protocol and 1 subject completed the study but did not dose titrate beyond 120 mg BID.

With regard to the gastrointestinal organ system, of the 14 HD subjects who completed 13 days of dosing (1 subject at 120 mg BID and 13 subjects at 180 mg BID), 4/14 (29%) experienced no nausea during the study and 7/14 (50%) experienced Grade 1 intensity nausea that was self-limited and only occurred at the initiation dose of 30 mg. One subject (1/14, 7%) experienced Grade 2 nausea starting from the 60 mg BID through the 180 mg BID dose. Three subjects (3/14, 21%) only developed nausea at the 180 mg dose level.

With regard to the nervous system AEs, of the 14 HD subjects who completed the 13 days of dosing, 5/14 (36%) did not experience somnolence, 4/14 (29%) experienced somnolence that was self-limited and only occurred at the initiation dose of 30 mg. With regard to AE intensity, two subjects (2/14, 14%) experienced somnolence of Grade 2 intensity at dosing levels above 30 mg BID. Only one drug-related Grade 3 AE (vertigo) was reported in one subject at the 240 mg dose which resolved completely following drug termination. No clinically relevant findings in vital signs, blood pressure (BP), ECGs or physical examinations were noted during the study. Oxygen saturation was also monitored via pulse oximetry as a safety precaution. The oximetry readings were taken at regular intervals during the daytime and continuously monitored during the nighttime hours over the 15 days of drug dosing and up to a maximal dose of 240 mg BID.

In both the HD and healthy subjects, no clinically significant decrease in daytime readings were recorded in the oximetry readings except in the one male HD subject previously mentioned who discontinued from the study at the time of the development of a pleural effusion. There was no clinically significant decrease in the nocturnal oxygen saturation level below the pre-dosing baseline nocturnal oxygen saturation level in any HD subject.

The Investigator Brochure and Section 5.4.4.4; Table 21 and Section 5.4.4.2.2; Table 17 summarize the AE profile of the TR01 HD subjects and healthy subjects respectively.

During the course of TR01, the 15 HD subjects that were enrolled were on multiple concomitant medications. Common concomitant medications included heparin, vitamin D, aspirin, iron, hyperphosphatemia management with sevelamar, erythropoiesis-stimulating agent, secondary hyperparathyroidism management with cinacalcet, neuropathic pain management with gabapentin; antihypertensive medications such as amlodipine (calcium channel blocker), carvedilol (beta and alpha-1 blocker), metoprolol (beta blocker), losartan (ACE inhibitor); gastrointestinal medications: omeprazole, pantoprazole, ranitidine and renal vitamins and supplements. These medications seem to be commonly used by HD patients both in the US and the EU (Schmid et al 2010). There was no clinically significant difference in the adverse event profile observed based on concomitant medication use or obvious pharmacodynamic interaction over the course of the study.

Data on Itch Intensity was obtained in an unblinded fashion from the HD subjects enrolled in the open-label single arm Study TR01 using a 0 (none) to 10 cm (maximal possible

intensity) itch Visual Analogue Scale (VAS) recording “worst itch” intensity. From a baseline mean daytime VAS of 4.4 ± 2.3 cm and nighttime of 2.8 ± 2 cm, the mean VAS decreased over a 13-day dosing period by -3.6 ± 2.5 cm and by -1.8 ± 2.1 cm, respectively.

Please see the Investigator Brochure for more details on the TR01 study.

3.3.3 Additional Nalbuphine HCl ER Tablet Clinical Data

In addition to the subjects in the TR01 study, a total of 331 subjects have been exposed to nalbuphine HCl during the course of 8 previous clinical studies.

Four Phase 1 studies were early biopharmaceuticals studies conducted in healthy subjects mainly for formulation selection and as such they support the safety of the drug product. In addition, two Phase 1 studies were conducted with the current clinical formulations and each consisted of a single dose study assessing the safety, tolerability, and PK of the current tablet formulations in the 30 mg -180 mg range.

A safety and efficacy analgesic study was conducted in subjects with dental-pain following third molar extractions following a single dose (placebo or 60 mg or 120 mg). The subjects were otherwise healthy male and female subjects. The study also contained PK-PD analysis demonstrating an analgesic dose-response relationship, with clear differentiation between the nalbuphine dose groups and placebo group.

Oxygen saturation was monitored via pulse oximetry as a safety precaution during Phase 1 studies and in the single dose third molar extraction dental pain treatment study. All subjects who received the drug had oxygen saturation levels within the 90%-100% range during the studies.

A safety and efficacy analgesic study was conducted in a patient population experiencing osteoarthritic related joint pain using the current nalbuphine HCl ER 60 mg tablet. The population was demographically older with the mean age of 57 years and a range extending from age 40-70 years. Subjects were dosed continuously for up to 3 weeks starting at 60 mg BID up to a dose of 180 mg BID. Subjects who tolerated the initial dosing were titrated up in weekly increments of 60 mg BID to the maximal dose of 180 mg BID. The AEs that developed mainly had their onset at the initiation of dosing with no new type of AE developing in any statistically significant incidence during the course of dose escalation.

In both genders, the most frequently reported adverse events were primarily in the Central Nervous System and Gastrointestinal organ system categories. A higher incidence of AEs was noted in females during week one of dosing with the gender asymmetry in AE generation lessening as a function of time. This difference in AE incidence may be related to the tendency of females to have higher plasma levels than males (about 1.7 and 1.3 fold higher for C_{max} and AUC, respectively).

In these eight clinical studies overall, the most frequently reported AEs in the single dose and multi-dose studies were CNS events, namely dizziness, headache, and somnolence. Gastrointestinal system AEs were mainly nausea and vomiting. Most of the AEs noted in the clinical study program were mild to moderate in severity.

In the case of single dose Phase 1 nalbuphine HCl ER tablet administration, there was a dose relationship to the incidence of AEs and there was minimal AEs observed at the 30 mg dose compared to initiating dosing at the higher doses. As a result, a titration to higher

doses from a starting dose of 30 mg was selected for subsequent studies that also included TR01 in order to improve the tolerability of the drug.

Section 5 of the Investigator Brochure summarizes the results of the clinical development program in detail.

4 STUDY OBJECTIVES

4.1 PRIMARY OBJECTIVE

The primary objective of the study is:

- To evaluate the safety and tolerability of nalbuphine HCl ER tablets during a drug treatment period of up to 50 weeks.

4.2 SECONDARY OBJECTIVES

The secondary objectives of the study are to evaluate the effect of nalbuphine HCl ER tablets on:

- To evaluate the safety of nalbuphine by achieved maintenance dose at the end of Treatment Week 4
- Assess skin lesion improvement using the metrics of the PAS
- Change from Baseline in Patient-Reported Outcome measures Worst (i.e., most severe itching over the past 24 hours) itch NRS, average itch intensity NRS, VRS (itchy, burning and stinging), MOS Sleep-R, ItchyQoL, HADS by the final Treatment Period Visit
- Change between Baseline and the final Treatment Period Visit in PBI-P
- A description of the percentage of patients utilizing various doses of nalbuphine HCl ER tablets by Study Week
- A description of the frequency and reasons for dose up- and down-titration and treatment discontinuation during the study
- Frequency and distribution by time on study of patients determined to meet failure-to-improve criteria
- Changes in the PRO measurements during the Washout Period after cessation of treatment of nalbuphine HCl ER tablets
- Time to first use of rescue medications and the number of days of use of rescue medications for itching
- To evaluate the daily changes in the Subjective Opiate Withdrawal Scale (SOWS) during the Washout Period after cessation of treatment of nalbuphine HCl ER tablets

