The incidence of AEs will be summarized through the presentation of proportions by MedDRA body system classification and preferred term. Vital signs and laboratory data will be summarized using continuous-based descriptive statistics (n, mean, SD, median, minimum, maximum). The extent and duration of use of rescue medications will be similarly summarized using descriptive statistics. Summary statistics for AEs with onset during the Observation Period will be separately summarized. No formal statistical analysis will be performed on safety outcomes; inferences, if any, will be derived through clinical review and interpretation.

TABLE OF CONTENTS

1	STUDY SYNOPSIS	5
	TABLE OF CONTENTS	13
	LIST OF TABLES	16
	LIST OF FIGURES	16
2	LIST OF ABBREVIATIONS	17
3	INTRODUCTION	19
3.1	PRURIGO NODULARIS AND STUDY RATIONALE	19
3.1.1	General Information on Prurigo Nodularis	19
3.1.2	Potential Mechanism of Prurigo Nodularis Pathophysiology	21
3.1.3	Rationale for Investigating Nalbuphine HCl ER in Prurigo Nodularis	24
3.2	NALBUPHINE	27
3.3	NALBUPHINE HCL ER TABLET CLINICAL DEVELOPMENT	28
3.3.1	Overall Summary	28
3.3.2	Clinical Study TR01 in Hemodialysis Patients and Healthy Volunteers	29
3.3.3	Additional Nalbuphine HCl ER Tablet Clinical Data	31
4	STUDY OBJECTIVES	32
4.1	PRIMARY OBJECTIVE	32
4.2	SECONDARY OBJECTIVES	32
4.3	EXPLORATORY OBJECTIVES	32
5	STUDY ENDPOINTS	33
5.1	PRIMARY ENDPOINT	33
5.2	SECONDARY ENDPOINTS	33
5.3	EXPLORATORY ENDPOINTS	33
6	NUMBER OF SITES AND PATIENTS	34
7	ESTIMATED STUDY DURATION	34
8	SELECTION CRITERIA	34
8.1	STUDY POPULATION	34
8.2	INCLUSION CRITERIA	34
8.3	EXCLUSION CRITERIA	35
9	STUDY PLAN	35
9.1	GENERAL STUDY DESIGN	35
9.2	RATIONALE FOR STUDY DESIGN	35
9.3	SAFETY MONITORING PLAN	37
9.4	RISK-BENEFITS	39
9.5	STUDY OVERVIEW	40
9.6	STUDY PROCEDURES	42
9.6.1	Visit 1a (Day 1 of Study Week 1)	43
9.6.2	Treatment Period (Treatment Weeks 1-50)	45
9.6.3	Observation Period (Extended Screening Weeks 1-12)	58
9.6.4	Transition to Treatment Period (Visit 1b)	59
9.6.5	Washout and Safety Follow-Up Period	61

9.6.6	Premature Discontinuation of Study Drug Follow-up Telephone Contact Visit	62
9.6.7	Early Termination Visit for Patients who Withdraw Consent.....	62
9.6.8	Unscheduled Visits	63
9.6.9	Schedule of Events.....	63
9.7	STUDY DRUG TREATMENT AND DRUG ACCOUNTABILITY.....	63
9.7.1	Study Drug Dosing	63
9.7.2	Down-Titration	66
9.7.3	Multiple Missed Doses	66
9.7.4	Overdose	66
9.7.5	Treatment Compliance.....	66

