5 STUDY ENDPOINTS

5.1 PRIMARY ENDPOINT

- A description of the incidence and nature of TEAEs during Treatment Weeks 5-50

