9.2 RATIONALE FOR STUDY DESIGN

The primary objective of this TR03ext study is to evaluate the safety of nalbuphine HCl ER tablets in patients with prurigo nodularis for up to 50 weeks on drug, followed by a two week washout period for a total of up to 53 weeks of study duration. The open label design allows all patients, who have completed the parent study TR03, an opportunity to receive active treatment for the assessment of the safety of nalbuphine HCl ER tablets over a longer term and follow the effect of skin lesion healing in addition to reducing itch. A maximum of 50 weeks on study drug was chosen as a reasonable time frame that would add substantially to the understanding of chronic use of nalbuphine HCl ER tablets chronic use in prurigo nodularis.

Metze et al (1999) reported that 9 out of 17 patients with PN who were treated with the mu antagonist medication naltrexone reported a decrease in pruritus intensity of at least 50%.

Reduced scratching as well as skin lesion healing was reported over a time period of up to 20 months on drug. Based on these clinical observations, TR03ext was designed to be of sufficient duration to observe potential anti-pruritic suppressive effects of study drug on scratching behavior and thus potentially skin lesion healing. Furthermore, the TR03ext study design anticipates potential sustained anti-pruritic effect that may outlast the actual dosing of study drug in TR03. Thus an Observation Period has been incorporated to follow patients whose Worst Itch NRS has been significantly reduced for up to 12 weeks in order to measure the durability of the anti-pruritic effect and to allow patients to receive study drug if pruritus intensity increases within the 12 week time period.

This study will also allow evaluation of a titration algorithm that mimics the manner in which opioid medications are often used in clinical practice (i.e., stepwise titration) to a tolerable dose with an improvement in worst itch intensity. To facilitate evaluation by achieved dose, the dose to which the patient has been titrated at the end of Treatment Week 4 will be maintained through Study Week 50, with the exception of two allowable down-titration (See [Table 3](#) for dosing schedule). Patients who require a third down-titration after Treatment Week 4 must be discontinued from the study.

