Patients can enroll into TR03ext and receive drug as early as approximately 2 weeks following their last dose of study drug in the parent study TR03. Approximately one-third of patients are expected to enter the study after having received placebo in TR03. These patients are expected to have a high level of pruritus intensity. On the other hand, some patients who have received active treatment in TR03 may still have either reverted to their original pruritic conditions or may have a residual anti-pruritic effects from the drug treatment even following the 2-week wash out period. To allow for various starting levels of pruritus intensity, patients who have Worst Itch NRS that is ≥ 5 will enter the Treatment Period upon completion of Visit 1a. Patients whose Worst Itch NRS score is < 5 will be entered into an extended screening period, no-treatment criteria Observation Period for up to 12 weeks or until they develop a higher level of pruritus (i.e., Worst Itch NRS ≥ 5), at which point they will transition to the Treatment Period upon completion of Visit 1b. All patients entering the Treatment Period, whether immediately upon study entry or following a period of time in the Observation Period, will initially be titrated to a dose that can be as high as 180 mg BID during the first 4 weeks of the Treatment Period (See [Table 3](#) for dosing schedule). Patients who continue in the Observation Period and maintain a Worst Itch NRS score of < 5 will be screen failed from the study at the end of the 12-week period. While patients remain in the Observation Period, they will not be considered as enrolled into the study, but as participating in an extended screening process until they are eligible for treatment.

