9.6.2.1.3 Telephone Contact Number 2 (TC2, Treatment Week 4)

The patient is to be contacted by phone and the following are to take place:

- record AEs

- reinforce compliance
- instruct the patient on dose titration/maintenance based on [Table 3](#)
- patients reporting intolerable side effects at their current dose should titrate down to a tolerable preceding dose and this should be record as the patient's maintenance dose
- patients at any dose who reported intolerable AEs for the previous week (Week 3 on drug) and continue to report intolerable AEs on this visit, should be discontinued from study drug and scheduled for the End of Treatment Visit, TV14 (See [Section 9.6.2.2.12](#) and [Section 11](#))

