9.7.1 Study Drug Dosing

Following enrollment, the patient will receive 30 mg open-label tablets. At each visit at which study drug is to be dispensed, enough study drug should be supplied to ensure a sufficient number of tablets until the next visit plus an additional 8 tablets to allow for visit windows and/or possibility of a missed visit. Bottles can be re-dispensed, as appropriate.

Study drug can be taken with or without food. Patients will be instructed to take the AM and PM Study Drug tablets at the same times of the day, approximately 12 hours apart, preferably with 240 mL (approximately 8 ounces) of water. If the patient does not take a particular dose at the planned time he or she may take it up to 2 hours later. For example, if a patient is taking the Study Drug at 9 AM and 9 PM but forgets to take the 9 AM dose, he may take the 9 AM dose as late as 11 AM. After that time, the patient should skip the 9 AM dose and, instead, take the regularly scheduled next dose at 9 PM.

The first dosing day will be on either Visit 1a or Visit 1b. Titration will be based on tolerability. If the patient is experiencing a study-drug related AE or an AE that may be

aggravated by study drug uptitration, the study drug dose should not be increased, regardless of the NRS score.

The Study Drug will be titrated during the Treatment Weeks 1 - 4, according to the schedule in [Table 3](#) to a final dose of 30 mg BID up to 180 mg BID. The dosing for Treatment Week 1 is further described in [Section 9.6.1](#) (Visit 1a) and [Section 9.6.4](#) (Visit 1b).

Patients will titrate to tolerability beginning with a 30 mg dose on Day 1 (Visit 1a or Visit 1b) with a dose increase of 30 mg BID not more often than every 3 to 4 days in order to attain steady-state plasma concentrations of nalbuphine at each dose.

The achieved dose attained as of the end of Treatment Week 4 will be maintained throughout the rest of the Treatment Period. This dose will be defined as the patient's "maintenance dose". A single dose reduction or dose hold per patient is permitted during Treatment Period at the investigator's discretion. If subsequent dose reductions or dose interruptions are needed, the Medical Monitor must be contacted. The duration of any dose hold must be discussed with the Medical Monitor.

Table 3: Dosing Schedule for TR03ext

Week of Treatment Period ¹ (TV or TC)	Day	Drug Tolerance		Discontinuation
		Acceptable	Unacceptable ³	
Week 1 (TV1/Visit1a /1b)	1	30 mg (PM dose)	--	

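### Safety by Week 4 achieved dose groups patients by an outcome of tolerability, and crude AE proportions ignore unequal time on drug, so the by-dose table may hide or reverse a dose relation and the Weeks 5-50 figure understates risk under continued treatment

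*Protocol*

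**What the plan says.** All references are to Protocol Version 2.0 unless stated.

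- **Grouping.** Section 4.2 lists as its first secondary objective "To evaluate the safety of nalbuphine by achieved maintenance dose at the end of Treatment Week 4". Section 9.2 gives the reason for holding the dose after Week 4: "To facilitate evaluation by achieved dose".
- **How the dose is reached.** Section 9.7.1 states "Titration will be based on tolerability", within a range of 30 to 180 mg BID, and bars an increase while a drug-related AE is present. At the Week 4 call (Section 9.6.2.1.3), patients with intolerable effects "should titrate down to a tolerable preceding dose", and that lower dose is recorded as the maintenance dose.
- **Later changes.** Section 9.6.2.2 and Table 3 allow two reductions in Weeks 5-50. The body of Section 9.7.1 speaks of one reduction or hold, with further ones referred to the Medical Monitor. These passages need reconciling. On either reading, the dose at AE onset can differ from the Week 4 dose.
- **Summary measure.** The synopsis states "The incidence of AEs will be summarized through the presentation of proportions by MedDRA body system classification and preferred term", followed by "No formal statistical analysis will be performed on safety outcomes; inferences, if any, will be derived through clinical review and interpretation".
- **Primary endpoint.** Section 5.1: "A description of the incidence and nature of TEAEs during Treatment Weeks 5-50".
- **Time on drug.** Sections 9.2 and 9.6.2.2 stop drug from TV3 (Week 5) onward in patients who fail to improve. Sections 9.6.5 and 9.6.6 then follow them through a washout visit at two weeks and a call at 30 days. Section 9.6.2 limits entrants from the Observation Period to 46 weeks.

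**The concern.** Two separate problems affect the safety tables.

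First, the Week 4 dose is a post-baseline result of how the patient tolerated the drug. Patients with AEs in titration are held or moved down, and those without go up. A table of AEs by that dose therefore sorts patients partly by their tendency to have AEs. Section 3.3.3 reports that AE incidence rose with dose in single-dose Phase 1 studies, so a flat or inverted table here could be read as reassurance about high doses. The protocol relies on clinical reading of the tables, and the text at hand gives no caution about this selection.

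Second, a crude proportion counts a patient stopped at Week 5 the same as one treated for 50 weeks. The primary endpoint covers Weeks 5-50 in a study whose objective is safety over up to 50 weeks. A reader is likely to take the proportion as the risk over that period.

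**Working it through.** The protocol derives no figure for either quantity, so there is nothing to reproduce. The checks below show direction and size under stated assumptions.

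**1. Selection into dose groups**

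Assumed inputs: 30% of patients are AE-prone, with a Weeks 5-50 AE risk of 60% against 20% for the others. Of the prone, 80% end at 90 mg BID or less; of the others, 20% do.

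- Share at or below 90 mg: 0.3×0.8 + 0.7×0.2 = 0.24 + 0.14 = 0.38. Share above: 0.06 + 0.56 = 0.62.
- No dose effect, true risk 0.3×0.6 + 0.7×0.2 = 32% at every dose. The table reads (0.24×0.6 + 0.14×0.2)/0.38 = 45% in the low group and (0.06×0.6 + 0.56×0.2)/0.62 = 24% in the high group.
- Risk truly 1.5-fold higher above 90 mg, so 32% against 48%. The table reads 45% against 1.5×23.9% = 36%: reversed.
- In this example any true ratio below 0.453/0.239 = 1.9 would be reversed.
- If proneness does not carry over, so that everyone has a 32% risk in Weeks 5-50, both groups read 32% and there is no bias.

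A simulation of tolerability-driven titration from 30 to 180 mg BID in 30 mg steps (lognormal patient susceptibility, 400,000 patients per scenario) gave the following Weeks 5-50 proportions, as 30-60 mg against 150-180 mg:

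| Hazard ratio, 180 v 30 mg | Susceptibility SD | Table shows | True |
|---|---|---|---|
| 1.0 | 0.75 | 39% v 26% | 28% v 28% |
| 1.65 | 0.75 | 41% v 37% | 29% v 39% |
| 2.72 | 0.75 | 43% v 50% | 30% v 51% |
| 2.72 | 1.25 | 60% v 46% | 34% v 52% |

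With SD 0 there was essentially no Weeks 5-50 distortion. If Weeks 1-4 AEs are counted, every patient below 150 mg has an AE in this model, because an AE is what lowers the dose.

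**2. Unequal time on drug**

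Assumed inputs: 50-week risk of 40% at constant hazard; a fraction f stops at a mean of Week 13; AEs are captured for 30 days (4.3 weeks) afterwards, as in Section 9.6.6; stopping is unrelated to AE risk.

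- h = -ln(0.6)/50 = 0.0102 per week.
- Risk observed in a stopper: 1 - exp(-17.3h) = 16.2%.
- Crude proportion = (1-f)×40% + f×16.2%, giving 33%, 28% and 23% for f = 30%, 50% and 70%.
- Restricted to the 46-week primary window: h = -ln(0.6)/46 = 0.0111, observed time 9 + 4.3 = 13.3 weeks, stopper risk 13.7%, giving 32%, 27% and 22%.

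For a plausible f, the only anchor is the TR01 itch change in Section 3.3.2 (mean fall 3.6, SD 2.5 by day; 1.8, SD 2.1 by night), from a different population over 13 days. A normal model gives Φ(-3.6/2.5) = 7.5% and Φ(-1.8/2.1) = 20% with no improvement at one visit. Over the 11 visits TV3 to TV13, with an assumed within-patient correlation of 0.5 to 0.9, 17% to 63% meet the rule at least once. The 70% case lies beyond that range.

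**3. Precision**

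Sixty patients over six dose levels is about 10 each. An observed 3/10 has an exact 95% interval of 7% to 65%.

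**The case against.** - **The study is descriptive.** No test is planned, and with about 10 patients per dose level little can be read as a sign. That stands, and it limits the consequence. But evaluation by achieved dose is a stated design purpose, and clinical reading of a selected table is no safer than a test of it.
- **Detail may sit elsewhere.** The supplied Version 2.0 text ends before Section 19, and no SAP was at hand. Either may add rates or attribute AEs by dose at onset. This point therefore rests on what the protocol fixes, the Week 4 grouping and crude proportions, and not on what is absent. A reader might infer that AEs after a reduction will be charged to the Week 4 dose; the documents do not say so.
- **The crude proportion is not wrong.** It validly describes AEs while treated under the stop rule. It understates only the risk under continued treatment.
- **Early onset.** Section 3.3.3 reports that AEs in the osteoarthritis study mainly began at the start of dosing, and Section 9.3 says gastrointestinal effects occur early. A front-loaded hazard makes the loss smaller than shown. This also stands.
- **Prior exposure.** Section 9.2 states "Approximately one-third of patients are expected to enter the study after having received placebo in TR03", from which a reader might infer that pooling with patients from active TR03 arms dilutes the incidence. The documents do not support this. They give no size for it, and the active share among treated patients is unknown: entrants with a worst itch score below 5 go to Observation and may never be treated, while placebo patients are expected to have high itch.

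**Conclusion.** The point holds in limited form. The Week 4 dose is selected by tolerance, so the by-dose safety table may hide or reverse a true dose relation. A reader might infer that reversal will occur, but it needs susceptibility to persist past titration or Weeks 1-4 AEs to be included, and a strong enough dose effect can outweigh it. Separately, the crude Weeks 5-50 proportion falls short of the risk under continued treatment. For a 40% risk it reads about 33% to 23% across the stopping shares tried, assuming constant hazard, a mean stop at Week 13, 30-day follow-up and stopping unrelated to AE risk. All shares and hazards are assumptions. This is worth correcting, but it does not invalidate the study.

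**What to change.** 1. For the by-dose safety objective, tabulate TEAEs by the dose being taken at onset, with patient-time at that dose as denominator. Keep titration (Weeks 1-4) separate from Weeks 5-50.
2. Beside the crude proportions, give exposure-adjusted rates or first-occurrence cumulative incidence by time on drug. State the assumption about early stopping: non-informative, or treated as a competing event.
3. Keep the Week 4 achieved-dose table as descriptive, with a sentence saying that its groups are selected by tolerance and are not a dose-response comparison.

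Tables by TR03 arm are optional.

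The change needs analysis programming only, since dosing and AE data are already collected. The price is more tables with small cells. Attribution by dose at onset reduces selection by tolerance but does not remove it, which is why the statement in item 3 is still needed.
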